5.6. Electrocardiography

Electrocardiogram findings (normal, abnormal) at baseline will be summarized.

5.7. Physical Examinations

Patients with at least 1 abnormal finding (overall) and abnormal findings for each category will be summarized at baseline.

5.8. Protocol Violations

Patients with at least 1 protocol violation for each category will be summarized.

5.9. Childbearing Potential

For female patients, information related to childbearing potential, contraception, and menopause will be collected at screening. Information will be provided in the patient data listings.

6. EFFICACY ANALYSIS

6.1. General

The ITT analysis set will be used as the default patient population for all efficacy variables, unless otherwise noted. Summaries will be presented by treatment group as randomized.

6.2. Primary Efficacy Variable(s) and Analysis

Note: For consistency, all variables related to or derived from the primary efficacy variable (clinical asthma exacerbations) are discussed within this section. This includes the secondary efficacy variables of moderate exacerbations, the subset of exacerbations requiring hospitalization or emergency department visits, and the analysis of time to first exacerbation, all of which are otherwise listed in Section 6.3 (Secondary Efficacy Variable(s) and Analysis).

6.2.1. Variable Definition

The primary efficacy variable for this study is the frequency of CAEs per patient during the 52-week treatment period. CAE is defined as a clinically judged deterioration in asthma control as determined by the investigator and as evidenced by new or worsening asthma signs or symptoms based on the patient history, asthma control diary, physical examination, and/or ambulatory or clinic visit assessment of lung function AND that results in a medical intervention, including at least 1 of the following:

- use of systemic corticosteroids (oral or injection) or at least a doubling from a stable maintenance oral corticosteroid dose for at least 3 days
- asthma-specific hospital admission
- asthma-specific emergency department visit

Additional medication and/or medical intervention that would satisfy the CAE definition occurring within 7 days of the last day of a prior CAE event will be considered as part of the same event for analysis purposes.

The CAE start and stop dates will be collected in order to determine the exacerbation duration. The start date of a CAE will be the start date of the initial medical intervention (eg, use of systemic corticosteroids [oral or injection] or at least a doubling from a stable maintenance oral corticosteroid dose for at least 3 days, asthma-specific hospital admission, or asthma-specific emergency department visit, whichever comes first). The stop date is the last day of systemic corticosteroids or the last day of an asthma specific hospitalization or emergency department visit, whichever is later. For patients who are on a stable maintenance oral corticosteroid dose and receive at least a doubling of that dose for 3 days, the stop date is when they return to their baseline dose. For patients receiving a new use of oral corticosteroids or at least a doubling from their stable maintenance oral corticosteroid dose for at least 3 days that did not return to baseline, a CAE stop date will be the day that they have been on a stable dose for at least 10 days.

6.2.2. Primary Analysis

The primary analysis of frequency of CAEs will be analyzed using the general linear model (GLM) for data from the negative binomial distributions that is commonly referred to as the negative binomial (NB) regression model. The primary NB model will include the treatment group, randomization stratification factors (age and blood eosinophil categories, as defined in Section 2.4), and the number of exacerbations in the previous year as model factors and an offset variable. The offset variable will be calculated as the logarithm of follow-up duration minus the summed duration of exacerbations during the follow-up. Age and blood eosinophil categories will be based on data recorded in the clinical database.

The ratio of CAE rate between the treatment groups and its 95% confidence interval (CI) will be estimated from the NB model. Treatment effect will be evaluated using the likelihood based chi-square test. Clinical asthma exacerbations that occur between the first dose of study drug and 2 weeks after the end of treatment/early withdrawal visit will be counted towards the CAEs for analysis.

The primary analysis will incorporate data from all randomized patients. The analysis will include all exacerbations observed over 52 weeks, for patients who completed the 52 week treatment period and for patients who withdrew from treatment earlier than 52 weeks but from whom the sponsor was able to collect data post withdrawal. For early withdrawal patients that the sponsor will fail to retrieve data post withdrawal despite all attempts to contact the patient, a multiple imputation will be performed for the frequency of exacerbation post withdrawal. The multiple imputations will utilize the post withdrawal data observed for patients who withdrew early and for which the sponsor succeeded to retrieve the data. The methodology and algorithm used for imputations is described in [Appendix A](#).

The following sample Statistical Analysis Software (SAS®) code pertains to the primary efficacy analysis of CAEs.

```
proc genmod data=<<>>;
  class treatment strata1 strata2;
  model cae=treatment strata1 strata2 nexac /dist=negbin link=log offset=log_futime;
  estimate "CAE rate ratio" treatment 1 -1;
  lsmeans treatment /diff exp cl;
  ods output lsmeans=<<>>;
  ods output lsmeandiffs=<<>>;
run;
```

A frequency distribution bar graph will be provided for the number of CAEs by treatment group.

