2.3. Sample Size and Power Considerations

The primary efficacy variable for this study is the frequency of CAEs per patient during the 52-week treatment period. The study will be considered positive if the primary efficacy measure indicates a statistically significant treatment effect of reslizumab versus placebo at the respective predefined significance level.

Power calculations were based on the below assumptions:

- Negative binomial (NB) distribution for the number of exacerbations with a mean of 2.9 exacerbations per patient per year for the placebo group
- Dispersion parameter of 1.2
- Treatment effect of 45% between the reslizumab group and the placebo group
- Alpha level of 0.05

Based on the assumptions above, 225 patients per group (450 total) will provide >90% power to detect significant treatment effect of reslizumab over placebo in the reduction of exacerbation rate. The sample size was increased beyond the sample size required to provide 90% power in order to allow sufficient number of patients to assess safety and immunogenicity and to ensure adequate enrollment in the adolescent subset. The current sample size also provides higher power for other efficacy endpoints.

Patients with blood eosinophil levels of 300/ μ L to <400/ μ L will be limited to no more than 30% of patients (60 patients per treatment group).

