3.4.4. Asthma Background Medication

Patient classifications based on Global Initiative for Asthma (GINA) guidelines ([GINA 2015](#)) will be derived. Selected efficacy endpoints including CAEs and pre-bronchodilator FEV₁ will be examined for the following medication classes taken at baseline. Medications at baseline will be defined as those taken at the time of randomization.

- **GINA 4 – ICS/LABA+ (Yes, No)**
Note: “Yes” is defined as patients taking ICS (medium or high-dose); and LABA or leukotriene or xanthine as a second controller; and no OCS use
 - ICS/LABA (Yes, No)
Note: “Yes” is defined as patients taking ICS (medium or high-dose); and LABA as a second controller; and no OCS use
 - High-dose ICS/LABA (Yes, No)
Note: “Yes” is defined as patients taking ICS (high-dose); and LABA as a second controller; and no OCS use
 - Medium-dose ICS/LABA (Yes, No)
Note: “Yes” is defined as patients taking ICS (medium-dose); and LABA as a second controller; and no OCS use

- **GINA 5** – OCS (Yes, No)
Note: “Yes” is defined as patients taking OCS

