3.4.5. Other Subgroups

Selected efficacy endpoints including CAEs (primary), pre-bronchodilator FEV₁, AQLQ+12, ACQ-6, and blood eosinophils will also be examined for the following demographic subgroups:

- Gender (Male, Female)
- Race (White, Black, Asian, Other; Black, non-Black)
- Region (North America, Eastern Europe, Western Europe, Latin America, Asia/Pacific, Middle East/Africa; US, non-US)
- Phadiatop result (Positive, Negative)
- Age of asthma onset (<40, ≥40 years)
- BMI (<30, ≥30 kg/m²)
- ADA status (Positive, Negative) – for reslizumab-treated patients only

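### The primary exacerbation model omits baseline maintenance oral corticosteroid use; adding it costs one parameter and gives slightly better precision and protection against chance imbalance

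*SAP*

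**What the plan says.** - **Primary model (SAP 6.2.2).** "The primary NB model will include the treatment group, randomization stratification factors", followed in the same sentence by the number of exacerbations in the previous year. The sample code agrees: treatment, two strata, prior-year count and a log-time offset. The offset is follow-up time less the summed duration of exacerbations. Protocol 9.5.6.1 names the same covariates.
- **Stratification (SAP 2.4).** Age group and screening eosinophil group only.
- **OCS users are eligible.** Protocol 4.2, criterion h, allows maintenance OCS for asthma up to a dose limit.
- **OCS use enters the endpoint (SAP 6.2.1).** The steroid criterion for a CAE is use of systemic corticosteroids or "at least a doubling from a stable maintenance oral corticosteroid dose for at least 3 days". For maintenance users whose dose was doubled, the event ends when they are back on their baseline dose. For other patients it ends with the last day of systemic steroids, or of the hospital or emergency stay if later.
- **OCS use is already classified.** SAP 3.4.4 has a yes/no class, where yes "is defined as patients taking OCS", based on medication at randomisation. Region is a subgroup as well (SAP 3.4.5): "Region (North America, Eastern Europe, Western Europe, Latin America, Asia/Pacific, Middle East/Africa; US, non-US".
- **Other primary-endpoint analyses.** None of the five sensitivity analyses in SAP 6.2.3 adds OCS use. The subgroup analyses in SAP 6.2.5 use on-treatment data, and the separate model with a subgroup term serves to give an interaction p-value.

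**The concern.** OCS use at baseline marks more heavily treated disease, and here it also changes how an event is recognised and how long it lasts. Both the count and the exposure in the primary model can therefore depend on it. The prior-year count will pick up part of this, but it is not built to capture a different event threshold or stop rule during the trial.

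Neither stratification nor adjustment controls OCS use, so a chance difference between arms adds to the sampling error of the rate ratio, and any precision available from it is left unused. No planned analysis gives an OCS-adjusted estimate on the all-data basis of the primary analysis. What is at stake is the width of the interval and the answer to a likely question if the arms happen to differ in OCS use.

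**Working it through.** **1. Reproduce the planned power.** Inputs from SAP 2.3: negative binomial counts "with a mean of 2.9 exacerbations per patient per year for the placebo group"; k = 1.2 for the dispersion; a 45% reduction, that is, a rate ratio of 0.55; a significance level of 0.05, taken as two-sided (SAP 4.3); 225 per arm; one year of follow-up.

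- Reslizumab rate = 2.9 × 0.55 = 1.595.
- Var(log RR) = (1/2.9 + 1/1.595 + 2 × 1.2)/225 = (0.345 + 0.627 + 2.4)/225 = 0.01499, so SE = 0.1224.
- Power = Φ(|ln 0.55|/0.1224 − 1.96) = Φ(4.884 − 1.96) = 99.8%.

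This agrees with the stated >90% (SAP 2.3, Protocol 9.1) and >99% (Protocol synopsis).

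**2. Ceiling on the OCS gain, ignoring the prior-year count.** Let p be the OCS share and R the CAE rate ratio for OCS users against non-users. Neither is in the documents; the assumed ranges are p = 10-20% and R = 1.5-2.0. The squared coefficient of variation explained is CV² = p(1−p)(R−1)²/(1+p(R−1))², and the residual dispersion is k = 2.2/(1+CV²) − 1.

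- p = 0.10, R = 1.5: CV² = 0.0204, k = 1.156, SE = 0.1208, a fall of 1.3%.
- p = 0.20, R = 2.0: CV² = 0.1111, k = 0.980, SE = 0.1141, a fall of 6.8%.

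The formula overstates the gain. In one case that also included region (10% OCS, R = 1.5, regional CV 0.2), it gave a 3.8% fall, while fitted models on 400 simulated trials gave 1.3%. Simulations of OCS alone, without the prior-year count, gave falls of 0.3-2.7% over the assumed ranges.

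**3. Gain over the SAP's model, which has the prior-year count.** Simulated trials of 225 per arm with the count included gave a fall in SE of roughly 0.2-2.4%. The result depends on how much of a patient's exacerbation tendency the count carries, which is also an assumption. Where it carried 30-70%, the fall was 0-0.5%; where it carried only OCS and regional information, 0.5-2.1%. In sample-size terms, 1/0.998² = 1.004 and 1/0.976² = 1.050, like 0.4-5% more patients.

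**4. Chance imbalance.** Take p = 15% and R = 1.8.

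- SD of the between-arm difference in OCS share = √(2 × 0.15 × 0.85/225) = 3.4 percentage points.
- One SD, split as 16.7% against 13.3%: (1 + 0.8 × 0.167)/(1 + 0.8 × 0.133) = 1.1336/1.1064 = 1.025.
- On the log scale this is about 0.024, and 0.024/0.1224 = 0.2 SE.

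This is an upper figure, because it is for a model without the prior-year count, which may absorb part of the imbalance.

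**5. If the true effect is smaller.** With a 30% reduction, SE = √((1/2.9 + 1/2.03 + 2.4)/225) = 0.1200 and power = Φ(0.3567/0.1200 − 1.96) = 84.5%. Applying the same proportional falls of 0.2-2.4% gives about 84.6-86.1%.

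**The case against.** The case for leaving the model alone is strong on size. The model is prespecified and valid, and it already contains a direct measure of each patient's exacerbation tendency. Randomisation makes an OCS imbalance ordinary sampling error that the confidence interval covers. The OCS share and its rate ratio are assumed. The dose-doubling threshold could lower the counted rate in OCS users and offset their greater severity, so a rate ratio near 1, with almost no gain, is possible. OCS use is not ignored either: background medication classes are summarised to assess comparability of the arms (SAP 5.3), and OCS is a CAE subgroup.

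All of that stands as a limit on the size. It does not supply an OCS-adjusted estimate for the all-data primary analysis, which no planned analysis gives.

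Three stronger readings are tempting, and the documents do not support them.

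- **That the rate ratio is biased.** A reader might infer this from the unstratified factor. Randomisation rules it out; only precision and chance imbalance are affected.
- **That region belongs in the primary model too.** The trial spans about 30 countries and every route to a CAE is a treatment or admission decision, so this is plausible. But the documents give no regional rates. Under an assumed between-region SD of 0.2-0.4 in log rate, OCS plus region lowers the SE by about 0.6-5.6% with the prior-year count in the model. That takes up to five more parameters, and the SAP has no rule for merging sparse regions.
- **That the hospitalisation/emergency and moderate-exacerbation analyses lose in the same way.** Both are on-treatment (SAP 6.2.4, 6.2.7), the moderate analysis uses a different offset, and neither is defined by the dose-doubling criterion. Their rates are not given, so no gain can be calculated, and SAP 6.2.4 expects few admissions or emergency visits taken singly.

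**Conclusion.** The point holds as a minor improvement to the primary model. Baseline OCS use is collected, classified, unstratified and tied to the endpoint definition, and it is absent from the model. Adjusting for it lowers the SE by roughly 0.2-2.4% if 10-20% of patients use OCS and their rate is 1.5-2.0 times that of non-users; the gain is near zero if OCS is weakly prognostic. A one-SD imbalance moves the rate ratio by at most about 2.5% in the case worked above. The planned power and the validity of the test are unaffected.

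The range rests on assumed OCS inputs, on how much the prior-year count already explains, and on reading the dispersion of 1.2 as the value before covariates, which the documents do not specify.

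**What to change.** Before unblinding:

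- Add baseline OCS use (yes/no at randomisation, SAP 3.4.4 definition) as a covariate in the SAP 6.2.2 model and its sample code. The refit on each imputed dataset (Appendix A, Step 4) follows automatically, because it uses the primary model's covariates.
- Keep the current model as a sensitivity analysis in SAP 6.2.3.
- If an estimate adjusted for region is wanted, list it in SAP 6.2.3 as supportive only, with the grouping fixed on blinded data.
- Record the change in SAP section 10, which now reports no changes to the protocol-specified analyses. The protocol's allowance for extra covariates (Protocol 9.5.6.2) sits under the secondary analyses, so the primary model needs its own entry.

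The cost is SAP wording and one extra parameter with about 450 patients. No new data are needed.

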### **3. STUDY DESIGN**

#### **3.1. General Design and Study Schema**

This is a 52-week, Phase 3, multicenter, randomized, double-blind, placebo-controlled study to evaluate the safety and efficacy of reslizumab, at a fixed dose of 110 mg, administered sc every 4 weeks in patients aged 12 years and older with asthma and elevated blood eosinophils, who are inadequately controlled on at least a medium total daily ICS dose and a second asthma controller.

Evidence of inadequate asthma control will include a history of at least 2 exacerbations requiring systemic corticosteroids (oral or injection) in the previous 12 months, a suboptimal screening ACQ-6 score ( $\geq 1.5$ ), and persistent symptoms during run-in on the patient's usual asthma controller regimen. At least one of the historical exacerbations must have been previously documented in the medical or pharmacy record; additional exacerbations may have been documented in either the medical or pharmacy record, or may be documented by the study site at the time of screening history. For all exacerbations, which fulfill inclusion criterion 'c', the approximate dates of systemic corticosteroid therapy and the name of the systemic corticosteroid taken should be recorded in source documents. The study consists of a screening period of up to 2 weeks to satisfy essential screening inclusion criteria (ie, confirmation of asthma with elevated blood eosinophils), a minimum 3-week run-in period on usual care to establish the patient's baseline level of control and a 52-week double-blind treatment period. If the patient enrolls in an available open-label, long-term safety study, then adults (age 18 years and older) may wait to complete the early and late follow-up visits until the end of the open-label study; however, adolescents (ages 12 to <18 years) should complete the early follow-up visit at 12 weeks as part of this current study before starting an open-label study.

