2.2.1. Primary Efficacy Endpoint

The primary efficacy endpoint is the frequency of clinical asthma exacerbations (CAEs) per patient during the 52-week treatment period. Refer to Section 6.2.1 for additional details regarding the definition of CAE.

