4.3. Multiple Comparisons and Multiplicity

A fixed sequence multiple testing procedure will be implemented to test the primary and secondary variables while controlling the overall type I error rate at 0.05. If the resulting two-sided p-value from the primary comparison is ≤ 0.05 , then the next comparison of interest (first secondary variable) will be interpreted inferentially at 0.05. This process continues through the secondary variables until either all comparisons of interest are interpreted inferentially, or until the point at which the resulting two-sided p-value for a comparison of interest is > 0.05 . At the

point where $p > 0.05$, no further comparisons will be interpreted inferentially. The hierarchy of endpoints is as defined in Section 6.3.1.

No multiplicity adjustments will be made for other efficacy and exploratory analyses.

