The negative binomial model will be fitted to the complete set of data for each of the 10 datasets using the same covariates that were used for the primary analysis. The model will include

log(follow-up time) as an offset variable, either excluding/including the summed duration of exacerbations, depending on the analysis. For patients with imputed number of exacerbations, complete follow up of 1 year is assumed. The summed duration of exacerbations will be calculated as summed duration of any exacerbations observed prior to treatment withdrawal + 8 days for each additional (imputed) exacerbation. The assumption of 8 days for the duration of exacerbations is consistent with the minimal duration of exacerbation as derived previously in the BREATH IV program.

Step 5: Multiple imputation and associated combining rules applied to propagate imputation uncertainty (Little and Rubin 2002).

The output datasets from Step 4 will contain inferential statistics for each imputation iteration. The SAS[®] procedure PROC MIANALYZE will be used to generate an overall p-value and 95% CI for the treatment difference; results will be exponentiated back to their original scale.

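### The primary analysis gives two incompatible counting windows for exacerbations (52 weeks, and the end-of-treatment visit plus 2 weeks) and no end date for the offset

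*SAP*

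**What the plan says.** - **Endpoint.** SAP 2.2.1 defines the primary endpoint as CAE frequency "per patient during the 52-week treatment period".
- **First counting rule.** SAP 6.2.2 takes CAEs between first dose and "2 weeks after the end of treatment/early withdrawal visit will be counted towards the CAEs for analysis".
- **Second counting rule.** The next paragraph of 6.2.2 says: "The analysis will include all exacerbations observed over 52 weeks". Protocol 9.5.6.1 has both rules as well, so the SAP's precedence over the protocol does not settle the matter.
- **Offset.** SAP 6.2.2 uses the log of follow-up duration less time spent in exacerbation. It gives no end date for follow-up.
- **Imputed patients.** In SAP Appendix A, Step 4, "complete follow up of 1 year is assumed". Step 3 adds their simulated events to events observed in the treatment period. SAP 3.1 ends that period 4 weeks after the last dose for patients who stop early, not 2 weeks after a visit.
- **Related analyses.** The on-treatment analysis (SAP 6.2.3) and time to first CAE (SAP 6.2.6) both end at the week-52 visit for completers, with no added 2 weeks.
- **After week 52.** Protocol 3.1 says "adults (age 18 years and older) may wait to complete the early and late follow-up visits until the end of the open-label study". In Protocol Table 2, the next exacerbation assessment after visit 17 is that early follow-up visit. Protocol 9.10 says placebo patients who roll over will receive reslizumab.

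**The concern.** The two rules in SAP 6.2.2 cannot both define the primary count. Two programmers could follow the text faithfully and build different event counts and different offsets.

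The added 2 weeks also lie outside the defined endpoint, in a period where data collection changes. An adult who rolls over may have no scheduled exacerbation assessment in this study, whereas an adolescent is expected to complete the 12-week follow-up visit first. Some placebo patients could already be receiving reslizumab. No rule stops counting at the first open-label dose.

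At stake is whether events and exposure cover the same interval for every patient in the primary model, and whether that interval is the randomized, blinded one.

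**Working it through.** **Inputs.** SAP 2.3 gives "a mean of 2.9 exacerbations per patient per year for the placebo group", dispersion k = 1.2, a 45% reduction (ratio 0.55, so a reslizumab rate of 2.9 × 0.55 = 1.595), 225 per group, and "Alpha level of 0.05". SAP 4.3 makes the test two-sided: "If the resulting two-sided p-value from the primary comparison is" at or below 0.05. The documents give no dropout, imputation or rollover shares, so those below are assumptions. Event rates are taken as constant over time.

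**1. The plan's power figure.** Wald formula on the log rate ratio, with t in years:

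Var = [1/(2.9t) + 1/(1.595t) + 2 × 1.2] / 225

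- t = 1: Var = (0.3448 + 0.6270 + 2.4)/225 = 0.01499, SE = 0.1224. Then |ln 0.55|/SE = 0.5978/0.1224 = 4.88, and 4.88 − 1.96 = 2.92, so power is 99.83%. This agrees with more than 90% in SAP 2.3 and more than 99% in the protocol synopsis.
- The same formula with 200 per group gives 99.6%, the figure in the superseded text shown in SAP Table 9.
- t = 54/52: power is 99.84%. The window does not affect the sample size.

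**2. Size of the tail.**

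- 2/52 = 3.8% of a completer's time. With the ±7-day window on visit 17, counting ends between weeks 53 and 55.
- Placebo events: 225 × 2.9 × 2/52 = 25.
- Reslizumab events: 225 × 1.595 × 2/52 = 14. Both assume that all 225 complete.

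**3. Events counted to week 54, with different offsets.**

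- Offset also to week 54 for observed patients: no bias, because the model compares rates.
- Offset at 52 weeks for everyone, all counted to week 54: both rates rise by 54/52 = 1.038 and the ratio stays 0.55.
- Offset at 52 weeks for observed patients, with a share f of patients imputed at 1 year of events over 1 year: the arm's rate is multiplied by (1 − f) × 54/52 + f. Equal f in both arms leaves 0.55.
  - f = 0% placebo, 20% reslizumab: 0.55 × 1.0308/1.0385 = 0.546.
  - f = 20% placebo, 0% reslizumab: 0.55 × 1.0385/1.0308 = 0.554.

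**4. Open-label drug in the placebo tail.** Let p be the share of placebo patients dosed open-label at week 52, and q the fraction of the full effect reached over the 2 weeks:

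ratio = 54 × 0.55 / {52 + 2 × [1 − p + p × (1 − 0.45q)]}

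- p = 0.5, q = 0.5: 29.7/53.775 = 0.552.
- p = 0.9, q = 1: 29.7/53.19 = 0.558. This needs 90% rollover on the day of the visit and full effect at once.

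**The case against.** The strongest reply is that this is a wording matter with almost no numerical consequence. A negative binomial model with a log follow-up offset exists to handle unequal follow-up. The rate inflation is common to both arms and cancels in the ratio. The open-label overlap dilutes the effect and so works against the drug. The prespecified on-treatment analysis already ends at the week-52 visit for completers. All of this stands as an argument about size. It does not make the two rules compatible or supply the missing end date. Nor does the on-treatment analysis isolate the tail, because it also removes events after treatment discontinuation.

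Two stronger readings are tempting, and the documents do not support either.

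- **That the rule discards data from patients who stop treatment early.** A reader might take the early withdrawal visit in SAP 6.2.2 to be the visit at which treatment stops, and infer that events more than 2 weeks later are lost. But Protocol 4.4.1 makes that an unscheduled discontinuation visit, with visits continuing to week 52. Protocol 3.16.4 has these patients continue through the end-of-treatment visit. Protocol 4.4.2 ties the early withdrawal visit to complete withdrawal from the study. SAP 3.1, the second paragraph of 6.2.2 and the ET1 category in Appendix A all keep their data. What remains is a term that should be defined, because the discontinuation visit uses the early-withdrawal assessments.
- **That placebo patients are on open-label reslizumab in weeks 52 to 54.** Protocol 3.1 permits deferral of follow-up visits for adults who enter an available open-label study. It gives neither a first-dose date nor a rollover share. Protocol 3.16.4 and SAP 5.2 allow rollover patients to count as having completed at week 52, so it is unclear whether their later CAEs would be captured here at all. Nothing says that the randomized assignment is revealed on rollover.

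**Conclusion.** The point holds as an inconsistency in the primary endpoint definition. The visit-plus-2-weeks rule misfits a 52-week endpoint, the offset has no end date, and observed and imputed patients can be counted over different lengths of time.

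The numerical effect is small. The ratio moves from 0.55 to at most about 0.558 if 90% of placebo patients roll over at week 52 with immediate full effect. It lies between 0.546 and 0.554 if the offset is not extended and imputed shares differ by 20 percentage points between arms. It does not move if offset and count match and no open-label drug is given in the tail. Power stays above 99.8%. These figures rest on constant event rates and on assumed rollover and imputation shares.

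The documents do not support a claim of lost patient-time among early stoppers. The discrepancy is worth correcting before unblinding because it concerns the primary count and is cheap to remove.

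**What to change.** 1. In SAP 6.2.2, count CAEs that start from first dose to the week-52 visit (visit 17, or the nominal week-52 date if that visit is missed), and none after the first open-label dose.
2. Use that same end date for the offset of observed patients and for the missing exposure T_M in Appendix A.
3. Keep the 1-year follow-up for imputed ET2 patients, and take their observed events up to the point where T_M starts. Ending their offset at last contact would put a full year of observed plus imputed events over a shortened denominator.
4. State that for patients who stop treatment but stay in the study, the window runs to week 52 and not to the treatment discontinuation visit.
5. Add to SAP 6.2.3 a sensitivity analysis that includes the 2-week tail, with an offset extended to match.
6. Record the departure from Protocol 9.5.6.1 in SAP section 10, which now reports no changes.

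The cost is edits to four places in the SAP before unblinding. The primary count loses the late events: about 25 placebo and 14 reslizumab CAEs at planning rates if all patients complete. Power goes from 99.84% to 99.83%.
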